4.2. Designation of Study Eye(s) and Randomization

For subjects with unilateral uveitis, the study eye will be the affected eye. For subjects with bilateral uveitis, the study eye(s) will be the eye(s) meeting eligibility criteria. If both eyes satisfy eligibility criteria, both eyes may be enrolled in the study. In a subject with both eyes eligible for enrollment, randomization of the subject's second study eye may occur no sooner than study Day 7 of that subject's first study eye.

Following confirmation of eligibility at Day 1, eyes will be randomly assigned (2:1) to receive the FAI insert using either the Mk II inserter or the Mk I inserter, respectively. Randomization assignments will be administered through a central Interactive Web Response System (IWRS). Randomization will be stratified on the basis of the investigator administering the treatment. The randomization schedule will be prepared using a blocked randomization and will be generated by an independent statistician. Only those subjects who have been enrolled in the study will have data recorded on the electronic case report forms (eCRF).

4.3. Masking of Study Subjects

Treatment assignments will be masked to study subjects. Any non-study eye may receive any standard treatment at the discretion of the Investigator.

4.4. Analysis Population

4.4.1. Intent-to-Treat (ITT) Population

The ITT population will include all eyes randomized into the study; analyzed as randomized. A given subject may have more than one eye included in the ITT population. All eyes in the ITT population will be analyzed according to the treatment they were randomized to receive and not according to what they actually received, in the event there is a discrepancy.

4.4.2. Safety Population

The safety population will include all eyes randomized into the study; analyzed as treated. A given subject may have more than one eye included in the Safety population. All eyes in the Safety population will be analyzed according to the treatment actually received and not according to the treatment they were randomized to receive, in the event there is a discrepancy.

5. Subject Disposition

5.1. Disposition

Disposition will be summarized for the ITT population at the subject level and at the eye level.

Disposition summarized at the subject level will include the number and percentage of subjects for the following categories: number of eyes randomized (one, two), subject randomization (one eye randomized to the MK I Inserter, one eye randomized to the MK II Inserter, both eyes randomized to the MK I inserter, both eyes randomized to the MK II Inserter, and one eye randomized to the MK I inserter and one eye randomized to the MK II Inserter), subjects who completed the study, subjects who discontinued from the study, and reasons for study discontinuation. The reason includes the following: adverse event, lack of efficacy, lost to follow-up, death, subject voluntarily withdrew, physician decision, sponsor decision, and study cancelled. Percentages will be based on the number of subjects who have at least one eye randomized.

Disposition will also be summarized at the eye level for the ITT population, summarizing eyes in the Safety population, eyes that completed the study, eyes that discontinued the study, and the reason for premature study termination by treatment group and for all treated eyes. Percentages will be based on the number of eyes randomized.

All disposition data will be presented in a listing.

5.2. Protocol Deviations

All protocol deviations will be reviewed and assessed as to significance prior to each database lock. The protocol deviations will be summarized by treatment group for the ITT population.

Protocol deviations will be presented in a listing for the ITT population.

6. Demographics and Baseline Characteristics

6.1. Demographics

Demographics will be summarized by treatment group and at the subject level for all subjects for the ITT population and Safety populations. Summaries will be generated for the Safety population only if there are randomized eyes that do not receive treatment. Summaries by treatment group will be based on the number of randomized (ITT) or treated eyes (Safety); therefore a subject who has both eyes randomized (treated) will be counted more than once, "repeating" the subject level demographics information once for each treated eye. Percentage for the by treatment summaries will be based on the number of randomized eyes and percentages for the total subjects summary will be based on the number of subjects who have at least one eye randomized (treated).

The demographics data consist:

- Age (years) calculated using the date of the informed consent and date of birth
- Sex
- Race
- Ethnicity
- Iris color
- Height (cm)
- Weight (kg)
- Body Mass Index (BMI) (kg/m²) calculated as (body weight in kilograms) / (height in meters)²

Age (years), height (cm), weight (kg), and BMI (kg/m²) will be summarized as continuous variables. The number and percentage of eyes/subjects by age category ($\leq 20, 20 - 40, 40 - 60, \geq 60$), sex (Male, Female), race (White, Black, Asian, American Indian or Alaska Native, Native Hawaiian or Other Pacific Islander, and Other) and ethnicity (Hispanic or Latino, Not Hispanic or Latino), and iris color (Black, Brown, Hazel, Green, Blue, Grey, and Other) will also be reported.

Demographics data will be presented in a listing for the ITT population.

6.2. Baseline Ocular Characteristics

Baseline ocular characteristics will be summarized by treatment group and for all treated eyes for the ITT and Safety populations. Summaries will be generated for the Safety population only if there are randomized eyes that do not receive treatment.

The baseline ocular characteristics to be summarized include:

- Treated Eyes (OD, OS)
- Duration of uveitis (years) calculated as (screening date date of onset of uveitis +1)/ 365.25
- Number of recurrences in the last 12 months
- Lens status
- Presence of cataract (if with lens status of phakic)
- History of vitrectomy procedure(s)
- Prior incisional anti-glaucoma surgeries
- Baseline BCVA (letters)
- Baseline IOP (mmHg)

Duration of uveitis, baseline BCVA (letters), and baseline IOP (mmHg) will be summarized as continuous variables. For partial uveitis onset dates, a missing month will be imputed as January and a missing day will be imputed as the first of the month. The number and percentage of eyes by duration of uveitis (< 2 years, 2 to 5 years, > 5 years), number or recurrences in the last 12

months (<= 2, >2), lens status (phakic, aphakic, and pseudophakic), presence of cataract (if with lens status of phakic), and history of related procedure(s) and surgeries will also be reported.

Baseline ocular characteristics will be summarized for randomized eyes only. Summaries will be presented at the eye level. Percentage will be based on the number of randomized eyes (ITT) or treated eyes (Safety).

All collected baseline ocular characteristics data for all eyes will be presented in a listing for the ITT population.

6.3. Medical History

6.3.1. Non-ocular Medical History

Non-ocular medical history and current non-ocular conditions will be summarized by treatment group for each body system for the ITT population. Body systems will be included as recorded on the eCRF. The non-ocular medical history data will be also summarized for all subjects at the subject level. Summaries by treatment group will be based on the number of randomized eyes; therefore a subject who has both eyes randomized will be counted more than once, "repeating" and counting the non-ocular history once for each treated eye. Percentage for the by treatment summaries will be based on the number of randomized eyes and percentage for the total subjects summary will be based on the number of subjects who have at least one eye randomized.

Non-ocular medical history data, including specific details on the condition/diagnosis and start/end dates, will be presented in a listing for the ITT populations.

6.3.2. Ocular Medical History

Any clinically significant ocular conditions within the past 12 months prior to Screening will be recorded on the eCRF. Ocular medical history data, including specific details on the condition/diagnosis, location (OS, OD, and OU), study eye(s) designation, treatment required, and start/end dates, will be presented in a listing for the ITT populations.

6.4. Inclusion and Exclusion Criteria

Prior to randomization, the investigator will assess whether the eye fulfills all the requirements of the inclusion and exclusion criteria outlined in the protocol. If an eye does not fulfill all of the requirements, the specific inclusion criterion not met or exclusion criterion which was met will be recorded on the eCRF. This information and whether the sponsor granted a waiver will be presented in a listing.

7. Treatments and Medications

7.1. Prior and Concomitant Medications

Prior and concomitant medication will be summarized by drug class and preferred term after coding with WHO Drug (WHO201209 version or higher) Dictionary terms.

All summaries will be provided for ocular medications and non-ocular medications, separately. Systemic steroids and immunosuppressants that have been prescribed for uveitis will be

summarized as ocular medications, but are not considered prohibited in this study. Summaries will include the total number of medications, the number and percentage of eyes or subjects receiving at least one medication, and the number and percentage of eyes or subjects receiving a medication summarized at the summarized by ATC level 1 term, ATC level 2 term, and preferred term. Eyes and/or subjects may receive more than one medication per ATC level 1 category, ATC level 2 category, and preferred term. At each level of summarization, an eye or subject is counted once if the eye or subject received one or more medications.

All prior and concomitant medication, including pre- and post-ocular procedure medications will be presented in listings for the Safety population.

7.1.1 **Prior Medications**

Prior medications are defined as those medications with a recorded end date prior to the initiation of study treatment.

Prior non-ocular medication will be summarized by treatment group for each drug class and preferred term for the Safety population. The prior non-ocular medication data will be also summarized for all subjects at subject level. Summaries by treatment group will be based on the number of treated eyes; therefore a subject who has both eyes treated will be counted more than once, "repeating" the non-ocular medication and counting once for each treated eye. Percentages for the by treatment summaries will be based on the number of treated eyes and percentages for the total subjects summary will be based on the number of subjects who have at least one eye treated.

Prior ocular medication will be summarized by treatment group and for all treated eyes for each drug class and preferred term for the Safety population. Percentages will be based on the number of treated eyes.

7.1.2 Concomitant Medications

Concomitant medications are defined as those medications which are taken on or after the initiation of study treatment (Day 1). This includes medications which start prior to Day 1 but continue while the subject is on treatment.

Concomitant non-ocular medication will be summarized by treatment group for ATC level 1 term, ATC level 2 term and preferred term for the Safety population. The concomitant nonocular medication data will be also summarized for all subjects at the subject level. Summaries by treatment group will be based on the number of treated eyes; therefore a subject who has both eyes treated will be counted more than once, "repeating" and counting the non-ocular medication once for each treated eye. Percentages for the by treatment summaries will be based on the number of treated eyes and percentages for the total subjects summary will be based on the number of subjects who have at least one eye treated.

Concomitant ocular medication will be summarized by treatment group and for all treated eyes for each drug class and preferred term for the Safety population. Percentages will be based on the number of treated eyes.

An additional summary of concomitant medication for each of the specified reasons for medication (recurrence of uveitis, treatment emergent AE, increased IOP, cataract, other) will be reported as well.

7.1.3 **IOP Lowering Medications**

The number and percentage of eyes requiring IOP lowering medication to control elevated IOP will be summarized by treatment group and for all treated eyes. Any systemic medications will be summarized as received in both eyes. IOP lowering medications will be identified as those medications with a reason for medication of "Increased IOP". Incidence will be summarized through 12 months and for 3 month time intervals through 12 months.

The number of medications (one, two, \geq three) required to achieve adequate IOP control will also be included in the summary. IOP medications will be counted at the "ingredient" level. For example, if the subject is receiving COSOPT (which contains two ingredients TIMOLOL MALEATE and DORZOLAMIDE HYDROCHLORIDE) and TIMOLOL MALEATE at the same time, the subject will be included in analysis as receiving two medications.

A single medication must be used for a minimum of 7 days. Multiple medications must be used concurrently for a minimum of 14 days. A subject does not need to be taking the same medication(s) over a given period to be counted for analysis. For example, if a subject is taking Medication A from days 50 to day 55, then Medication B from days 56 to 62, the patient will be counted as receiving 1 medication to control IOP, because the subject required at least one IOP medication/ingredient for 7 consecutive days, even though each medication/ingredient was used for less than 7 days. In a similar example, if a subject was receiving Medication A from days 50 to 60, Medication B on days 61 to 70, and Medication C on Days 52 to 70, then the subject will be counted in the analysis as receiving 2 medications, because the subject received two unique medications/ingredients over days 52 to 70.

Because medications can start and stop at various times in the analysis periods (up to month 3, month 3 to month 6, etc.) a medication will be counted in a given period if the start date(s) for the required number days of consecutive use (7 days for a single medication, 14 days for multiple medications) occurs within the period, even if the end of the 7 or 14 days of consecutive use falls after the end of the given analysis period. Medication(s) which begin in one analysis period and continue to the "next" analysis period will be counted in the "next" analysis period only if the medication(s) were received for at least 7 or 14 days (for single or multiple medications, respectively) in the "next" period.

A summary of IOP lowering medications will also be presented by history of incisional surgery to control elevated IOP (History of Incisional Surgery, No History of Incisional Surgery). All summaries will be performed using the Safety population for the final analysis at Month 12 only.

7.2. Ocular Surgeries

All ocular surgeries during a subject's participation in the study will be recorded on the eCRF.

A summary of surgery/procedure for each of the specified reasons (recurrence of uveitis, treatment emergent AE, increased IOP, cataract, other) will be reported. Summaries will be provided by treatment group and for all treated eyes for the Safety population.

Ocular surgery data, including details on the procedure, eye, start date, and reason for the surgery, will be presented in a listing for the Safety population.

7.2.1 Surgical Intervention to Control Elevated IOP

The number and percentage of eyes requiring any surgical intervention to control elevated IOP will be summarized by treatment group and for all treated eyes. Ocular surgeries with a reason of "Increased IOP" will be included in the summary. Surgery data will be reviewed to ensure all IOP surgeries including those with "Other" indication are also identified using the specification text. Incidence will be summarized overall through 12 months and for 6 month time intervals through 12.

A summary of incidence of surgical interventions to control elevated IOP will also be presented by history of incisional surgery to control elevated IOP (History of Incisional Surgery, No History of Incisional Surgery). All summaries will be performed using the Safety population for the final analysis at Month 12 only.

A listing of all subjects requiring surgical interventions to control elevated IOP will be provided. This listing will include details relating to the IOP-lowering surgical intervention (procedure, eye, study eye designation, and date procedure performed), demographic and baseline ocular characteristics including BCVA and IOP, and the last available BCVA and IOP values as of the data cut-off.

7.2.2 Cataract Surgeries

The number and percentage of eyes requiring cataract surgery will be summarized by treatment group and for all treated eyes. Only eyes which are indicated as phakic at study entry will be included for analysis. Ocular surgeries with a reason of "Cataract" will be included in the summary. Incidence will be summarized overall through 12 months and for 6 month time intervals through 12 months. All summaries will be performed using the Safety population and percentages will be based on the number of phakic eyes in the Safety population. Analysis will be performed for the final analysis at Month 12 only.

7.3. Study Treatments

Fluocinolone acetonide (FA) is the active ingredient in the FAI insert. The FAI insert is an injectable intravitreal sustained-release FA delivery system pre-loaded into an injection device and is administered as an intravitreal injection through the pars plana. For this study, the FAI insert will be provided in one of two sterile preloaded inserters: the Mk I inserter or the Mk II inserter. The FAI insert is designed to release FA for a period of 36 months at a nominal rate of approximately $0.2 \ \mu$ g FA/day.

The Mk I inserter is a sterile, pre-loaded, modified syringe that uses a 25 gauge XX-thin wall

needle to penetrate the conjunctiva and sclera; the needle is not retracted after intravitreal injection has been completed. The Mk I inserter has been used previously in clinical study PSVFAI-001.

The Mk II inserter is a sterile, pre-loaded applicator that uses a 27 gauge standard wall needle to penetrate the conjunctiva and sclera; the needle is retracted during intravitreal injection.

Data related to the study treatment procedure will be presented in a listing for the Safety population.

7.3.1. Extent of Exposure

Duration of insert (days) is defined as the total number of days a study eye is exposed to study drug and will be presented as the total number of days from the injection date (Day 1) to either the FAI insert removal date, for those eyes which have the insert removed while in the study, or the last visit date (date of insert removal or last visit - the date of injection + 1) as recorded on the End of Study/Early Termination page. If the last visit date on the End of Study/Early Termination page is missing, or if a subject is lost to follow-up, the latest available visit date will be used. Duration of insert at Day 7 is defined similarly to overall insert duration, using either the FAI insert removal date, if removal occurred prior to Day 7 visit date, or the Day 7 visit date as the cut-off date. If a subject's Day 7 visit date occurs later than the data cut off for the Day 7 analysis (upper limit of Day 7 visit window) then the upper limit of the Day 7 visit date will be used as the end date of the insert duration.

Duration of insert up to Day 7 (or Month 12) will be summarized by treatment group and for all treated eyes for the Safety population. The duration of insert will be classified into following categories: ≤ 7 days, 8 to 28 days, 29 to 90 days, 91 to 360 days, and ≥ 360 days and the number and percentage of eyes in each duration category will be presented for the Safety population.

Duration of study participation (days) is calculated as date of last visit as recorded on the End of Study/Early Termination page – date of Day 1 visit + 1. If the last visit date on the End of Study/Early Termination page is missing, or if a subject is lost to follow-up, the latest available visit date will be used. Duration of study participation at Day 7 is calculated as the date of Day 7 visit – date of Day 1 visit + 1. If a subject's Day 7 visit date occurs later than the data cut-off for the Day 7 analysis (upper limit of Day 7 visit window), then the upper limit of the Day 7 visit date will be used as the end date of participation.

Duration of study participation up to Day 7 (or Month 12) will be summarized by treatment group and for all subjects at the subject level for the Safety population. The durations of study participation will be classified into one of the following categories: <= 7 days, 8 to 28 days, 29 to 90 days, 91 to 360 days, and >= 360 days and the number and percentage of eyes or subjects in each duration category will be presented for the Safety population. Summaries by treatment group will be based on the number of treated eyes; therefore a subject who has both eyes treated will be counted more than once, "repeating" and including the duration of subject participation once for each treated eye. Percentages for the by treatment summaries will be based on the

number of treated eyes and percentage for the total subjects summaries will be based on the number of subjects who have at least one eye treated.

Duration of insert and duration of study participation will be presented in a listing for the Safety population.

8. Utilization Analysis

Utilization analyses will be performed by treatment group, at Day 1 based on the questionnaires from Investigator and the Observer (Appendix 13.2).

All primary and secondary utilization endpoints will be analyzed using the ITT population.

Data related to the utilization will be presented in a listing for the ITT population.

8.1. Primary Utilization Endpoint

The primary utilization endpoint is defined as the proportion of intravitreal insertion procedures that are assessed by the Investigator as satisfactory. A satisfactory procedure is defined as one receiving a score from the Investigator as either Very Easy (VE), Easy (E), or Routine (R), according to the following categories:

- Very Easy (VE)
- Easy (E)
- Routine (R)
- Difficult (D)
- Very Difficult (VD)

If more than one inserter is used for the same eye, the results from the first inserter will be used for completing the questionnaires and analysis. Comments related to the second inserter will be presented in a listing. Any injector which penetrates the eye but does not deliver the FAI insert into the eye will be scored as Very Difficult for analysis.

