7.2. Number of Subjects

A total enrollment of approximately 30 eyes is planned for this study. Enrollment of approximately 25 subjects is expected, and will continue until:

- at least 20 and 10 study eyes each have been treated using the Mk II and Mk I inserters, respectively, and
- at least 10 different investigators each have performed at least one administration procedure.

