When count data are presented, the percentage will be suppressed when the count is zero in order to draw attention to the non-zero counts. A row denoted "Missing" will be included in count tabulations where specified on the shells to account for dropouts and missing values. For by treatment summaries, the denominator for percentages will be the number of eyes in each category in that treatment within the analysis population of interest, unless otherwise specified. For summaries for all subjects for data summarized at the subject level, the denominator for percentages will be the number of subjects who have at least one eye within the analysis population of interest, unless otherwise specified.

Unless otherwise specified, baseline will be defined as the last non-missing evaluation prior to or on the date of treatment injection (Day 1). The study day will be calculated as assessment date – date of treatment injection (Day 1) + 1. Study day for non-ocular events and assessments will be determined using the date of treatment in the first treated study eye. Study day for ocular assessments for the first treated eye will be determined using the date of treatment in the first treated study eye. If the second eye is also treated, study day for the ocular assessments in that eye will be based on the date of treatment in that eye. If the second eye is not treated, study day for ocular assessments in that eye will be based on the date of treatment in the treated study eye.

For all utilization and safety analyses, analysis visit windows will be used for assigning assessments to an analysis visit, as follows:

Scheduled Visit	Target Day	Visit Window (Days)		
Screening	-60 to 0	Not applicable		

Day 1	1	Not applicable
Day 7	7	4 to 10
Day 28	28	14 to 42
Month 3	90	69 to 111
Month 12	360	332 to 388

Only those assessments which are assigned to an analysis visit will be included in the summary tables and figures which are presented by visit. If there are multiple assessments assigned to the same visit window, the observation to be used for analysis will be determined as follows:

If there is only one observation falling into a defined visit window, then that observation will be flagged for inclusion in by-visit analyses.

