If there is more than one observation falling in a defined visit window and one of the observations was made in a "scheduled" study visit (e.g., day 7, day 28, Month 3, etc.) and the other observation(s) was made in an unscheduled visit, then the observation from the scheduled study visit will be used for by-visit analyses.

If there is more than one observation falling into a defined visit window and all observations are from unscheduled visits, then the earliest observation with non-missing data for a given assessment will be used for by-visit analyses.

All assessments will be presented in the data listings.

The Day 7 analysis will include all assessments with a start day on or before the upper limit of the Day 7 visit window (study day 10). The analysis at Month 12 will include all data in the database.

Subjects may have more than one eye randomized to treatment; therefore, for summaries counting patients by treated eye, a subject may be included more than once in a given summary. The same subject may be included more than once in the same treatment group if both eyes are randomized to the same inserter. Similarly, a subject may be counted more than once in the total eyes column if both eyes are randomized.

Subjects will be counted at most once for total subject summaries even if the subject has both eyes randomized.

Eyes not receiving assigned treatment and non-study eyes will have all safety data listed and will be included in selected AE and SAE summaries only. In the listings, randomized eyes that did not receive treatment will be grouped separately by their randomized treatment assignment (i.e., Mk I inserter - Not Treated, Mk II inserter - Not Treated). Non-randomized eyes which do not receive treatment will be grouped in listings. Percentages for Safety population summaries will be based on the number of eyes that received treatment.

All analyses will be conducted using SAS Version 9.2 or higher.

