8.1.1. Primary Utilization Analysis

The primary utilization analysis will compare the proportion of intravitreal insertion procedures that are assessed by the Investigator as satisfactory (i.e., VE, E or R), in the Mk I inserter and the Mk II inserter groups.

The number and percentage of eyes with satisfactory intravitreal insertion procedures will be presented, for the Mk I inserter and the Mk II inserter groups of eyes employing descriptive statistics including 95% confidence intervals using the exact binomial methodology. The difference in proportions, the 95% exact unconditional confidence interval for the treatment difference (Mk II vs Mk I) in proportions, and the Fisher's exact test p-value will also be provided, however this comparison is considered exploratory only as the study is not powered to detect a difference between the inserters.

The primary utilization analysis will be conducted after all eyes in the study have completed study Day 7 or have discontinued study participation.

The study will be deemed a success for the Mk II inserter if the following condition is met: The proportion of Mk II procedures scored as satisfactory is not numerically lower than the corresponding proportion of Mk I procedures.

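### Does the primary success rule leave open whether a randomized eye with no insertion attempt counts in the denominator?

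*SAP*

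**What the plan says.** SAP 8.1 defines the endpoint in terms of procedures: "The primary utilization endpoint is defined as the proportion of intravitreal insertion procedures that are assessed by the Investigator as satisfactory". The success condition in SAP 8.1.1 uses the same unit: "The proportion of Mk II procedures scored as satisfactory is not numerically lower than the corresponding proportion of Mk I procedures". Protocol 14.3.4.1 has the same rule.

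The analysis set is defined in eyes. SAP 8 (Utilization Analysis) says "All primary and secondary utilization endpoints will be analyzed using the ITT population", and SAP 4.4.1 says "The ITT population will include all eyes randomized into the study; analyzed as randomized". The default in SAP 4 for tables by treatment is that "the denominator for percentages will be the number of eyes in each category in that treatment within the analysis population of interest", unless another denominator is specified.

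The SAP allows for randomized eyes that are never injected. In the listings (SAP 4), "randomized eyes that did not receive treatment will be grouped separately by their randomized treatment assignment". For baseline tables (SAP 6.1), "Summaries will be generated for the Safety population only if there are randomized eyes that do not receive treatment". Neither provision concerns the primary endpoint. SAP 8.1 has one scoring override: an inserter that enters the eye without delivering the insert is rated Very Difficult.

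Protocol 7.2 continues enrollment until "at least 20 and 10 study eyes each have been treated using the Mk II and Mk I inserters, respectively", so an eye that is randomized but not injected does not count toward the target.

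**The concern.** On a literal reading, the number that decides success has two possible denominators. If procedures are counted, an eye with no attempt is absent. If all randomized eyes are counted, the same eye lowers the satisfactory proportion of an inserter that never touched it. Because enrollment stops on treated eyes, the study could end with, say, 21 Mk II eyes randomized and 20 injected.

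The rule has no margin, and group sizes of 20 and 10 make exact ties likely, so a single eye can tip the result. An uninjected Mk II eye could turn success into failure, and an uninjected Mk I eye could do the reverse. Only subjects are masked and the analysis follows Day 7, so an unwritten denominator could in principle be chosen with the ratings in hand.

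**Working it through.** **The plan's own figures.** SAP 4.1 gives the widest exact 95% intervals as 27.2% to 72.8% (10 of 20) and 18.7% to 81.3% (5 of 10). Clopper-Pearson limits from beta quantiles are 27.20% to 72.80% and 18.71% to 81.29%. Both reproduce, and the point at issue does not affect them.

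**Inputs.** 20 Mk II and 10 Mk I procedures performed (SAP 4.1, Protocol 14.1), and success if the Mk II proportion is at least the Mk I proportion (SAP 8.1.1). Two inputs are assumptions, because the documents give no value: a common true satisfactory rate p, and the number of eyes with no attempt.

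**Notation.** x1 is the number satisfactory of 10 Mk I and x2 the number satisfactory of 20 Mk II, giving 11 × 21 = 231 possible outcomes. Counting procedures, success is x2/20 ≥ x1/10.

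**One extra Mk II eye with no attempt.** Counting all randomized eyes, success becomes x2/21 ≥ x1/10. The verdicts differ only at ties, x2 = 2·x1 with x1 = 1 to 10, which is 10 of 231 outcomes. For example, 20/20 against 10/10 passes on procedures, but 20/21 = 95.2% against 100% does not on randomized eyes.

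P(differ) = Σ (x1 = 1 to 10) Bin(x1; 10, p) × Bin(2·x1; 20, p). At p = 0.90:

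| x1 | Bin(x1; 10) | Bin(2·x1; 20) | Product |
|---|---|---|---|
| 10 | 0.3487 | 0.1216 | 0.0424 |
| 9 | 0.3874 | 0.2852 | 0.1105 |
| 8 | 0.1937 | 0.0898 | 0.0174 |
| 7 | 0.0574 | 0.0089 | 0.0005 |

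The remaining terms are negligible, and the sum is 0.171. The chance of success moves from 0.560 to 0.389.

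**One extra Mk I eye with no attempt.** Success becomes x2/20 ≥ x1/11. Five outcomes differ: (x1, x2) = (6, 11), (7, 13), (8, 15), (9, 17) and (10, 19). At p = 0.90 the chance of success moves from 0.560 to 0.734.

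| Common p | Extra Mk II eye: P(differ) | Extra Mk I eye: P(differ) |
|---|---|---|
| 0.80 | 0.128 | 0.126 |
| 0.90 | 0.171 | 0.174 |
| 0.95 | 0.275 | 0.245 |

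**No such eye, or one in each group.** With none, the denominators are identical. With one in each, 20/21 and 10/11, 0 of 231 outcomes differ.

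**Allowing for how often such an eye occurs.** The figures above are conditional on exactly one such eye in one group. Let r be an assumed chance that a randomized eye is never attempted, with enrollment continuing until 20 and 10 attempts are made. The number of such eyes in each group is then negative binomial. Averaging over both groups at p = 0.90 gives an overall chance of differing verdicts of about 1% at r = 0.2%, 2.4% at 0.5%, 4.6% at 1% and 8% at 2%.

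**Which denominator the text supports.**
- SAP 3.2 bases analyses on individual eyes and labels the utilization evaluation that way. The protocol synopsis says the same of the primary endpoint.
- SAP 8.1 uses only the first inserter's result for an eye, so each attempted eye supplies exactly one procedure.
- SAP 8.1.1 presents the number and percentage of eyes with a satisfactory procedure.
- SAP 8 names the ITT set, SAP 4.4.1 defines it as all randomized eyes, and the SAP 4 default takes the denominator from that set.

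Read together, these point to ITT eyes.

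**The case for a change.** The best opposing case is that the text leans toward ITT eyes without settling the matter. The SAP 4 default gives way where another denominator is specified, and an endpoint worded in procedures could be read as specifying one. The default never says an unrated eye is not satisfactory. Its Missing row depends on table shells that are not among the documents, so whether they settle the point cannot be judged. Elsewhere the SAP states its denominator outright, as for eye-level disposition in SAP 5.1; section 8 does not. A sole success criterion ought to have its denominator fixed in advance, and one sentence would do it.

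The gap in wording stands, and so does the conditional arithmetic. What does not stand is the claim of two conflicting denominators, since the eye-based statements in SAP 3.2, 8.1 and 8.1.1 answer most of it. The untreated-eye provisions are contingency wording and do not predict that such eyes will occur.

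Making attempted eyes the primary denominator is also not a clear improvement. The Investigator knows the assignment before injecting, so leaving out eyes with no attempt gives up protection that ITT provides. Which denominator to make primary is a trade-off. A written score for a failed penetration, a rule for units damaged before use and a reworded questionnaire footnote would be further clarifications of the same kind.

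**Conclusion.** The concern does not call for a change. The plan is silent on how a randomized eye with no attempt enters the primary proportion, but its eye-based definitions and the ITT set point to one denominator, and no rule it states is shown to give a wrong result. This is a detail analysts would settle in programming the table.

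Given exactly one such eye in one group, and 20 and 10 procedures performed, the verdict could turn on the choice with probability about 0.13 to 0.28 for an assumed common rate of 0.80 to 0.95. Over assumed no-attempt rates of 0.2% to 2%, the overall chance at p = 0.90 is about 1% to 8%. Such an eye should be uncommon, because randomization follows eligibility confirmation at the same Day 1 visit as the injection.

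Most of the sensitivity to one eye comes from a zero-margin rule at this sample size: with equal inserters at p = 0.90, success has probability 0.56 even when no denominator is in doubt. The SAP already calls the study unpowered and the formal between-inserter comparison exploratory.
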